PROTOCOL TITLE: Comparing Web, Group, and Telehealth Formats of a Military Parenting Program

VERSION DATE: May 4, 2018

ABBREVIATIONS/DEFINITIONS

Include any abbreviations or definitions for key or technical terms you use in your protocol.

PROTOCOL TITLE: Comparing Web, Group, and Telehealth Formats of a Military Parenting Program

VERSION DATE: May 4, 2018

STUDY SUMMARY

Study Title	Comparing Web, Group, and Telehealth Formats of a Military Parenting Program
Study Design	Randomized Control Trial
Primary Objective	Advance the research on family-based prevention of negative outcomes for reintegrating Operation Enduring Freedom/Operation Iraqi Freedom personnel by evaluating different formats of a parenting program, After Deployment, Adaptive parenting Tools (ADAPT).
Secondary Objective(s)	
Primary Study Intervention or Interaction	Delivery of three different formats (in-person, tele-health and online) of ADAPT.
Study Population	National Guard and Reserve (former and present) personnel in MN and MI, and their families
Sample Size (number of participants)	360
Study Duration for Individual Participants	2 years

PROTOCOL TITLE: Comparing Web, Group, and Telehealth Formats of a Military Parenting Program

VERSION DATE: May 4, 2018

1.0 Objectives

1.1 Purpose:

The overarching goal of this study is to advance research on family-based prevention of negative child outcomes for reintegrating Operation Enduring Freedom/Operation Iraqi Freedom personnel by evaluating different formats of a parenting program, After Deployment, Adaptive Parenting Tools/ADAPT. The ADAPT program is based upon the Parent Management Training-Oregon Model/PMTO, but adapted for military deployed families. We will examine which of three delivery formats of ADAPT is most effective at reducing youth risk behaviors associated with negative childhood outcomes by improving parenting, child, and parent adjustment. There is a clear intent to benefit all subjects in this study (except surveyed teachers), including children.

We will conduct a three-group, two-site randomized trial to test the comparative effectiveness of ADAPT delivery approaches. The study will randomly allocate 360 NGR families to one of three conditions: (i) group-based web-enhanced ADAPT; (ii) individualized web-facilitated ADAPT; or (iii) self-directed web ADAPT.

Thus, specific aims are as follows:

1. Conduct a three-group, two-site randomized trial to test the comparative effectiveness of ADAPT delivery approaches
 - a. Families will complete a pre-intervention baseline assessment and post-intervention follow-up assessments at 6, 12- and 24 months.
2. Test the generalizability of ADAPT effectiveness across three delivery approaches using intent to treat (ITT) analyses
 - a. Test the value-added impact of group-based delivery relative to facilitated and self-directed web approaches
 - b. Comparative effectiveness will be tested by specifying a non-equivalence hypothesis for group based and individualized facilitated relative to self-directed web only

We hypothesize that (1) individualized web-facilitated parenting intervention will be equally effective as the group-based web-enhanced intervention, and (2) both individualized and group-based ADAPT will be more effective than a self-directed web-condition. Effective internet delivery methods will facilitate development of new approaches to engage military families separated by deployment, isolated by geographical location, and in need of strategies to deal with deployment and reintegration stressors, directly addressing limitations and barriers to access to evidence based prevention programs.

PROTOCOL TITLE: Comparing Web, Group, and Telehealth Formats of a Military Parenting Program

VERSION DATE: May 4, 2018

Analysis of Aim 1: ADAPT comparative effectiveness hypotheses will be tested using standard normal theory Analysis of Variance and multiple regression techniques in structural equation modeling (SEM) with a focus on growth curve analyses for follow up data. We will specify analyses to test Hypothesis 1: NGR families in both the ADAPT group-based condition and the ADAPT web-facilitated condition will show greater pre-post improvements in observed parenting, and parent, child, and couple functioning relative to the self-directed web condition; and Hypothesis 2: ADAPT group-based condition will be equally effective as the individualized ADAPT web-facilitated condition.

Analyses for Hypothesis 1 of Aim 1. We will employ standard normal theory pre-post Analysis of Variance and structural equation modeling (SEM) growth curve analyses for the long-term follow up. For the immediate pre-post analyses we will conduct a 3 group by 2 repeated measures Analysis of Variance for parenting, child, and couple functioning constructs focusing on the comparison of change across the Group Based, Individualized Facilitated, and Self-directed ADAPT conditions. The study randomly allocates 360 NGR families across the three conditions ($n = 120$ per group). For the 6-month assessment, we estimate a projected 5% attrition rate and over the 24-month follow up we expect roughly 15% attrition. In two prior PMTO randomized trials with intensive multiple-method family assessments, family retention was 88% and 86%, respectively, at 30-month follow-ups [2, 12]. In both of those studies, there were no differential rates of attrition between intervention and controls, there was less than 5% attrition by the immediate 6 month post-test assessment, and less than 15% attrition by the 24 month assessment. Using an alpha level of .05 and considering 5% attrition over the first 6 months, a pre-post design with 3 groups of 114, within subject $SD = 1$, and between groups $SD = .71$; the study is powered .81 to minimally detect a small group by time interaction effect ($ES = .12$), small time effect ($ES = .15$), and small group effect ($ES = .21$) for given parenting, child, couple or parent constructs.

Follow Up Analyses. For the intent to treat (ITT) analyses of long term follow up, we will specify latent growth models (LGM) recommended for long term effectiveness designs involving maximum likelihood SEM. LGMs have become more standard because they more reliably assess change. Growth models combine individual and group levels of analysis, taking into account mean growth and individual variation. Fixed effects (e.g., random assignment to ADAPT, parent and child gender) and time-varying random effects may be estimated using chronometric time weights. A model specifying an initial status latent variable (assessing variance in BL differences) and a linear slope latent variable (estimating individual differences in change over time), would be specified using factor weights of 1, 1, 1, 1, for the respective repeated measures, and factor weights of 0, 1, 2, and 4 for growth. The first step in LGM is to

PROTOCOL TITLE: Comparing Web, Group, and Telehealth Formats of a Military Parenting Program

VERSION DATE: May 4, 2018

identify the model that best characterizes patterns of growth. We can also specify an additional nonlinear quadratic factor, a higher order polynomial function to capture any nonlinearity. Accelerated or decelerated change would be specified with loadings fixed at 0, 1, 4, and 16. A sequential set of models tests the latent variances and model fit across a random intercept, linear growth, and quadratic model to determine the optimal growth pattern. The comparative effectiveness hypothesis for observed parenting is shown in Figure 2 as linear growth. Group Based and Web Facilitated will be contrasted to the Self-Directed omitted group. Analyses will test that the Group Based effect ($\beta_1 > 0$) and the Web Facilitated ($\beta_2 > 0$) will show greater 2-year improvements relative to Self-Directed. For the LGM in Figure 2 we estimated power using Mplus Monte Carlo simulations with 1000 replications. An advantage of this approach is the ability to incorporate specific patterns of expected attrition over time. For the figure in Figure 3, contrasts for Group Based and Web Facilitated were fixed at a mean of .33 and variance of .22 representing the random allocation across groups. The latent initial status intercept and latent growth factors were specified reflecting a commonly observed ratio of 5:1 for the variance components (Initial Status $\psi_2 = .5$ and SD = .70; and Linear Growth $\psi_2 = .1$, SD = .31). The effect size (ES) is then the ratio of group contrast mean differences in the latent growth factor divided by the SD for growth. A sample size of 306 (cumulative attrition of 15% over 2 years, specified as .05, .10 and .15 over time) obtained power of .98 respectively to detect small effects (ES=.10) for β_1 and β_2 relative to Self-Directed and likewise for child, couple, parent adjustment.

Analyses for Hypothesis 2 of Aim 1. To test whether the ADAPT Group Based and Web Facilitated have similar effects we will employ two related approaches to test whether ($\beta_1 = \beta_2$) for the paths shown in Figure 2. First, using the same model specification shown in Figure 2, we will further specify equality constraints in the LGM model to directly compare the relative magnitude of β_1 and β_2 . Second, we will conduct a one-sided non-inferiority test (i.e., a test of equivalence) for the intent to treat growth slope factor means and variances for the respective parenting, child, couple, and parent adjustment constructs; hypothesizing no differences between the Group Based and Web Facilitated conditions. We used the non-inferiority module in the Power Analysis and Sample Size program for the equivalence test of means using two one-sided tests for two groups of 102 (Group Based and Web Facilitated). The study is powered .82 using a .05 one-sided alpha when the reference mean = 1 and the comparison mean = 1, and the range of difference still results in the conclusion of equal means when the comparison group is plus or minus a quarter of a standard deviation of the reference mean ($\pm .25$ SDs). Finally, we will also examine dosage, participation, and variation in fidelity as potential moderators of group intervention effects.

PROTOCOL TITLE: Comparing Web, Group, and Telehealth Formats of a Military

Parenting Program

VERSION DATE: May 4, 2018

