assessments with the target 5-12 year old child, and complete parent-child observational tasks, and adult measures (approximately 100 minutes total). Families who prefer assessment outside the home may go to the local UMN or UM project office.

Note: Child care is offered to families for the siblings that are not participating in the research. In the event that child care staff are not available we will offer families a \$30 gift card stipend to provide their own child care during the in-home assessment.

5. Teachers will be contacted (at each time point) via secure, encrypted email, with an explanation of the study, and a copy of the parent's release of information. They will be directed to the study website to complete questionnaires. Teachers not responding will receive materials by mail, with follow-up calls. Teachers who do not want their compensation may choose to give the gift card back to ADAPT or to MCEC.

6. Following BL assessment, participants are electronically given random assignment to the G, W, or F study conditions, with 120 families assigned to each condition. The group condition will be run in three cohorts, with 2 groups of up to 10 families in each cohort of 20 families (up to 60 families in each of the two sites – i.e. 120 total, considerably more than we estimate will participate). In both online conditions, families may participate as they enter the study. However, given the necessity of running groups in cohorts and the need for equivalence in analysis, we will also assign individuals in the web conditions to a cohort.

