PROTOCOL TITLE: Comparing Web, Group, and Telehealth Formats of a Military Parenting Program

VERSION DATE: May 4, 2018

be completed during the baseline or follow-up, or study staff will provide funds for the family to travel to a local library, University, etc. to gain computer access.

Sources of Materials

- Research material obtained from human subjects will consist of data collected specifically for this study.

The data will include:

1. Web-based questionnaires filled out by families
2. Observational coding data based on videotaped parent-child interaction tasks completed by families
3. Short questionnaire packets filled out by families and teachers
4. Short surveys and web conference calls completed by expert panel members.
5. Audio and video tape of parent's response to KidVid (video of parenting tasks)

Measures and Assessments:

There are 4 assessments: Time 1- baseline (BL, prior to start of the intervention), Time 2 - six months post BL (post-intervention, given 4-5 month intervention at 3 sessions/month, allowing for holidays, etc), Time 3- 12 months following BL, and Time 4, 24 months after BL. Assessments are weighted to be gathered in the first year, (BL, 6, and 12 months) to gauge intervention effects immediately at posttest (i.e., T2) and at T3, which is when parenting and teacher report outcomes indicated change in prior studies. All measures (i.e., child, parent, and teacher report, and direct observations) will be gathered annually (T1, T3, T4), ensuring that teachers are different at each assessment. At T2, only parent report data will be gathered, online, (no in-home assessment) to minimize participant burden in Year 1, and because in prior studies observed parenting and teacher report outcomes indicated change at 12 months, while parent report indicated some change immediately posttest. Child self-report measures will be gathered (and were standardized with) children over age 8. Measures are summarized below:

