17.0 Data Management

17.1 Data Analysis Plan:

Descriptive analyses will be computed to determine the usability and acceptability of the delivery formats. We will examine family demographics, included age and gender of parent(s) and child(ren), as well as family structure. We will also compute descriptive analyses on the recruitment data, including the number and percentage of families expressing interest in the study, time to recruit families, the percentage of families screened who meet inclusion criteria. We will also examine retention data including weekly attendance, participants completing home practice assignments, as well as their reasons for absences or drop out.

Complex long-term follow up analyses will also be computed. We will employ standard normal theory pre-post Analysis of Variance and

PROTOCOL TITLE: Comparing Web, Group, and Telehealth Formats of a Military

Parenting Program

VERSION DATE: May 4, 2018

structural equation modeling (SEM) growth curve analyses. For the immediate prepost analyses we will conduct a 3 group by 2 repeated measures Analysis of Variance for parenting, child, and couple functioning constructs focusing on the comparison of change across the Group Based, Individualized Facilitated, and Self-directed ADAPT conditions.

For the intent to treat (ITT) analyses of long term follow up, we will specify latent growth models (LGM) recommended for long term effectiveness designs [110] involving maximum likelihood SEM. Fixed effects (e.g., random assignment to ADAPT, parent and child gender) and time varying random effects may be estimated using chronometric time weights. A model specifying an initial status latent variable (assessing variance in BL differences) and a linear slope latent variable (estimating individual differences in change over time), would be specified using factor weights of 1, 1, 1, 1, for the respective repeated measures, and factor weights of 0, 1, 2, and 4 for growth. The first step in LGM is to identify the model that best characterizes patterns of growth. We can also specify an additional nonlinear quadratic factor, a higher order polynomial function to capture any nonlinearity. Accelerated or decelerated change would be specified with loadings fixed at 0, 1, 4, and 16. A sequential set of models tests the latent variances and model fit across a random intercept, linear growth, and quadratic model to determine the optimal growth pattern [113].

17.2 Power Analysis:

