sing an alpha level of .05 and considering 5% attrition over the first 6 months, a pre-post design with 3 groups of 114, within subject SD = 1, and between groups SD = .71; the study is powered .81 to minimally detect a small group by time interaction effect (ES = .12), small time effect (ES = .15), and small group effect (ES = .21) for given parenting, child, couple or parent constructs.

17.3 Data Integrity:

Site coordinators and the project manager will oversee assessment technicians and conduct quality control checks regularly throughout the data collection process. If needed, additional training will be provided to assessment technicians. Video recordings of family interaction tasks will be monitored by the coding coordinator to ensure high quality and consistency across assessment technicians. Survey data will be cross-checked and cleaned shortly after in-home assessments are conducted to ensure data were collected accurately as well as resolve any discrepancies in key study variables (e.g., deployment status, marital status, gender, etc).

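### The 6-month parent-report comparison is fixed as a change-score test; adjusting for the baseline already collected would estimate the same arm contrasts more precisely

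*Protocol*

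**What the plan says.** Under Analyses for Hypothesis 1 of Aim 1 (Protocol section 1.0), the immediate comparison is set as follows: "For the immediate pre-post analyses we will conduct a 3 group by 2 repeated measures Analysis of Variance", "focusing on the comparison of change across the Group Based, Individualized Facilitated, and Self-directed ADAPT conditions". Section 17.1 commits to the same method: "For the immediate prepost analyses we will conduct a 3 group by 2 repeated measures Analysis of Variance".

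Sections 1.0 and 17.2 give its power as .81 at alpha .05 with 3 groups of 114 families (120 less 5% attrition), "within subject SD = 1, and between groups SD = .71", for an interaction effect size of .12, a time effect of .15 and a group effect of .21.

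Section 5.2 (Measures and Assessments) limits what is available at 6 months: "At T2, only parent report data will be gathered, online, (no in-home assessment". Parent self-report is also taken at baseline (section 5.2, item 3, and the measures table at the end of the protocol), and random assignment follows the baseline assessment (section 5.2, item 6).

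In the Group arm, families are taught in groups of five to ten (section 5.2, item 7). There are three cohorts of two groups at each of two sites (item 6), so 12 groups in all. Item 6 describes the 120 places as "considerably more than we estimate will participate".

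**The concern.** The stated target is the difference between arms in change. With one baseline and one follow-up value, the repeated-measures ANOVA tests this by subtracting the whole baseline from the follow-up score. When the two waves correlate below 1, that subtracts too much and adds baseline noise to the contrast. Because baseline precedes randomisation, a model that estimates the baseline slope targets the same arm contrasts with a smaller variance.

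At stake is the width of the immediate Group versus Self-Directed and Facilitated versus Self-Directed intervals. All three arms receive ADAPT content and the protocol calls the targeted effects small, so precision given up here matters.

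A lesser concern is that the ANOVA and its power treat the Group-arm families as independent, although those who attend share a taught group and its facilitators.

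**Working it through.** **Inputs.** N = 3 × 114 = 342; alpha .05; within SD 1; between SD .71; effect sizes .12, .15 and .21 (Protocol sections 1.0 and 17.2). Neither rho nor an intracluster correlation (ICC) is stated.

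**1. The plan's own figure.** Interaction: lambda = 2 × 342 × .12² = 9.85. With 2 and 339 df the noncentral F gives power .806, so the stated .81 reproduces.

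**2. Variance of the two analyses.** Let each wave have variance s² and the waves correlate at rho.
- Change score: variance 2s²(1 − rho).
- 6-month score adjusted for baseline: variance s²(1 − rho²).
- Ratio, adjusted to change: (1 − rho²) / [2(1 − rho)] = (1 + rho)/2, which is below 1 for every rho below 1.

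**3. What rho might be.** If .71 is the between-subject SD and 1 the within-subject SD, rho = .71² / (.71² + 1) = .504/1.504 = .335. Two things favour this reading. The group effect then has lambda = 342 × .21² / 1.504 = 10.03 and power .813, matching the stated .81. The growth-model power calculation in section 1.0 also uses an initial-status variance of .5 (SD .70). Neither is proof: the match uses the variance of a single wave, and the growth-model text gives no residual variance.

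**4. Power after baseline adjustment**, lambda = 9.85 / [(1 + rho)/2], df 2 and 338:

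| rho | variance ratio | lambda | power | families giving the precision of 342 change scores |
|---|---|---|---|---|
| .335 (from the SDs) | .668 | 14.75 | .94 | 228 |
| .5 (assumed) | .75 | 13.13 | .91 | 256 |
| .7 (assumed) | .85 | 11.59 | .87 | 291 |
| .8 (assumed) | .90 | 10.94 | .85 | 308 |

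The last column is 342 × (1 + rho)/2. Simulation at rho .335 gave .81 for the ANOVA and .94 for the adjusted model.

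**5. The time effect.** The definition nearest the stated power takes ES .15 as mean change over the SD of change: lambda = 342 × .15² = 7.70, df 1 and 339, power .79. Within one arm, lambda = 114 × .15² = 2.57 and power is about .36.

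**6. Taught groups (secondary).** With 12 groups of m attenders among 114 analysed Group-arm families, the variance of a Group contrast is multiplied by 1 + 12·m(m − 1)·ICC / (2 × 114). A nominal 5% test that ignores this has actual level 2[1 − Φ(1.96/√factor)]. The ICC values are assumptions.

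| ICC | level, m = 5 | level, m = 9 |
|---|---|---|
| .02 | 5.2% | 5.9% |
| .05 | 5.6% | 7.2% |
| .10 | 6.2% | 9.5% |

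Nine per group means 12 × 9 = 108 of the 114 families attending. The standard error ratio (√factor) runs from 1.01 to 1.05 with five attenders and reaches 1.17 at ICC .10 with nine.

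**The case against.** The strongest reply is that nothing here is an error. The ANOVA is unbiased under randomisation, holds its level when families are independent, answers the pre-post hypothesis directly and has the power claimed. All of that stands: this is a point about efficiency. It goes beyond preference because the protocol names the method twice and powers it, while the better model needs no further data.

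A second reply is that section 1.0 also mentions multiple regression, and that an unseen SAP may list covariates. The regression wording is general and names no baseline covariate for the 6-month comparison. The only other adjustment promised is for relationship status (section 9.1). This softens the point without removing it.

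A third is reach. The Aim 1 analysis is described "with a focus on growth curve analyses for follow up data", those models already include baseline as initial status, and observed, teacher and child-report outcomes are not collected at 6 months. This stands and sets the scope.

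A fourth is that the gain is modest if rho is high: 10% to 15% of the variance at .7 to .8. Averaging two parents' reports would probably raise rho. This also stands.

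Some stronger readings are tempting but not supported:
- A reader might take .71 as the SD of a family's two-wave mean. That makes rho nearly 0 and the variance gain about 50%. But with ES .21 scaled by that .71, group-effect power is about .94 (lambda = 342 × .21² = 15.08), not the stated .81.
- A reader might infer that the test is invalid or that .81 is wrong. Neither follows.
- A reader might infer serious inflation from the taught groups. That needs nearly full groups and a high ICC, whereas the protocol expects attendance below capacity.

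**Conclusion.** The point holds as a worthwhile efficiency improvement, limited to parent-report outcomes at 6 months. The planned test is valid and its .81 is correct for the interaction. Adjusting for baseline would raise power for the same effect to about .94 if rho is near the .33 suggested by the protocol's SDs, and to between .91 and .85 for assumed rho of .5 to .8. These figures rest on equal variances at the two waves, independent families and 5% attrition. The size of the gain depends on a correlation the protocol does not give; its direction does not. The growth models are not affected by this point.

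The taught-group matter is real but secondary. With about five attenders per group the level of a nominal 5% Group contrast is 5.2% to 6.2% over ICC .02 to .10. It approaches 9.5% only with nearly full groups and ICC .10.

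**What to change.** In Protocol sections 1.0 and 17.1, make the 6-month arm comparisons (Group versus Self-Directed, Facilitated versus Self-Directed) with a linear model of the 6-month score on arm and the same measure's baseline. State how two parents' reports from one family enter that score. Keep the pooled pre-post time test as a separate analysis. In sections 1.0 and 17.2, restate pre-post power over an assumed range of rho.

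As a secondary change, add a partially nested term for taught group in the Group arm with small-sample degrees of freedom (for example Kenward-Roger or Satterthwaite), treating families who never attend as singletons.

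The cost is wording and analysis code, with no new data or visits. The ANOVA's group main effect, which averages baseline and 6 months, gives way to the adjusted arm test. The pooled time test is unchanged, with power of about .79 at ES .15. Within-arm change, if reported, has power of only about .36 and should be presented as descriptive. The taught-group term widens Group-arm intervals slightly at the attendance the protocol seems to expect.

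### The 6-month pre-post test of Hypothesis 1, and its .81 power, concern a three-arm omnibus interaction rather than the two comparisons with Self-Directed that the hypothesis claims

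*Protocol*

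**What the plan says.** Hypothesis 1 is cited here as numbered under Analysis of Aim 1 in protocol section 1.1. It states that families in both the group-based and the web-facilitated condition "will show greater pre-post improvements in observed parenting, and parent, child, and couple functioning relative to the self-directed web condition". That is two directional comparisons, each against the same reference arm.

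Under Analyses for Hypothesis 1 of Aim 1, the immediate test is given as follows: "we will conduct a 3 group by 2 repeated measures Analysis of Variance for parenting, child, and couple functioning constructs". Its stated emphasis is on how change differs over all three arms together. Section 17.1 repeats this. No pre-post contrast of either active arm with Self-Directed is named.

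The power statement opens "Using an alpha level of .05 and considering 5% attrition over the first 6 months", assumes three groups of 114 with a within-subject SD of 1, and concludes "the study is powered .81 to minimally detect a small group by time interaction effect (ES = .12" (section 17.2, same figure in section 1.1).

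Two other parts of the protocol bear on the scope:
- Follow Up Analyses in section 1.1 contrasts Group Based and Web Facilitated with Self-Directed as the omitted group, in the direction of benefit. This is for 2-year improvement in the growth model and has its own power statement.
- Sections 5.2 (Measures and Assessments) and 5.3 limit the 6-month assessment to online parent report. Observed parenting is collected at baseline, 12 and 24 months.

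**The concern.** The test and the hypothesis ask different questions. The group-by-time interaction in a three-arm, two-occasion design is significant when the arms do not all change alike. That can happen because both active arms beat Self-Directed, because only one does, because the two active arms differ from each other, or because Self-Directed does best. Only the first is Hypothesis 1.

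Two things are at stake. A significant 6-month interaction could be reported as support for Hypothesis 1 when one active arm is no better than Self-Directed. And the only short-term power figure in the protocol does not give the chance of showing what the hypothesis says; for showing both comparisons, that chance is lower.

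**Working it through.** **Inputs (protocol section 1.1, Analyses for Hypothesis 1 of Aim 1).** 120 families per arm; 5% attrition by 6 months, so 120 × .95 = 114 per arm and 342 in all; alpha .05; within-subject SD 1; two occasions; interaction ES f = .12; stated power .81.

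**Step 1: reproduce the .81.** Noncentrality λ = N × T × f² / SD² = 342 × 2 × .12² = 9.85. With 2 and 342 − 3 = 339 degrees of freedom at alpha .05, the noncentral F gives power **.806**, which matches .81. Other readings do not match: 1 df on all 342 families gives .88, 1 df on one pair of arms (228 families) gives .72, and omitting the factor T gives .49. The .81 is therefore omnibus power.

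**Step 2: does that power distinguish Hypothesis 1 from its failure?** For change scores, λ = n Σ(τ − mean τ)² / 2, since the variance of a change is 2 × 1² = 2. Write the mean changes as (Group, Facilitated, Self).
- (D, D, 0), Hypothesis 1 true: squared deviations sum to D²(1/9 + 1/9 + 4/9) = 2D²/3.
- (D, 0, 0), Hypothesis 1 false: squared deviations sum to D²(4/9 + 1/9 + 1/9) = 2D²/3.

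λ is the same, so the omnibus power is the same .81. In the second case, the probability that both contrasts are significant in the right direction at two-sided .05 is only about .025.

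**Step 3: power for the contrasts at the same effect, equal active arms.**
- 114 × (2D²/3) / 2 = 38D² = 9.85, so D = .509.
- SE of a difference in mean change = √(2 × 2/114) = .187.
- Noncentrality per contrast = .509/.187 = 2.72. Equivalently its square is .75 × λ = 7.39, so the result does not depend on how ES is scaled once .81 has fixed λ.
- The contrasts share the Self-Directed arm and the arms are equal in size, so they correlate .5.

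A bivariate normal calculation and a simulation of 1,000,000 trials with pooled error agree to within .01:

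| Test level for each contrast | Each contrast | Both | Both, and omnibus F significant |
|---|---|---|---|
| Two-sided .05 | .77 | .65 | .645 |
| One-sided .05 | .86 | .77 | .72 |

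For scale, about 155 analysed families per arm (155/.95, or about 164 randomised) would give .81 for both contrasts at two-sided .05 and the same effect.

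**The case against.** The strongest reply has four parts.

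- **The directional contrasts are already in the protocol.** Follow Up Analyses in section 1.1 tests each active arm against Self-Directed and powers those paths. This stands, and it limits the point. A reader might infer that power for Hypothesis 1 as a whole is .65; the documents do not support that, because the long-term part has its own contrasts and power statement. It does not remove the point, because the hypothesis is worded as pre-post improvement and the pre-post analysis has its own test and power figure.
- **The .81 is labelled correctly.** Sections 1.1 and 17.2 call it power for a group-by-time interaction and nowhere say that a significant interaction proves Hypothesis 1. This stands: the figure is not misstated, it answers another question. A statistical analysis plan, which is not at hand, could name the contrasts, but the protocol's only short-term power figure would still be for the omnibus test.
- **The .65 rests on choices the protocol does not make.** Sidedness is not given for this test; the protocol says one-sided only for Hypothesis 2. One-sided, the joint figure is .77. A single contrast at two-sided .05 loses little (.77 against .81). So .65 is not an upper limit. A reader might also cite .34, the two-sided joint power if Facilitated gains half as much as Group at the same λ, but that pattern departs from the equal effectiveness posited in Hypothesis 2.
- **The omnibus F does no harm as a first step.** With three arms, an F test followed by unadjusted pairwise tests is a valid closed procedure. Gating costs almost nothing two-sided (.65 to .645) and somewhat more one-sided (.77 to .72). The documents give no ground for dropping the F test.

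The 6-month data are also parent report only, so the point does not reach observed parenting, the first outcome that Hypothesis 1 names.

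**Conclusion.** The point holds for the immediate pre-post part of Hypothesis 1, on parent-reported outcomes at 6 months. The protocol fixes and powers a 2-df interaction, while the hypothesis requires two specific comparisons to go the same way. A significant interaction does not establish the hypothesis.

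The shortfall against .81 is moderate. For showing both contrasts the probability is about .65 two-sided or .77 one-sided. For one contrast alone it is about .77 or .86, so one-sided it exceeds .81.

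These figures assume the protocol's own effect size and 114 per arm, equal active arms, no multiplicity adjustment (none is needed when both must succeed), and one construct at a time. They carry no conclusion about the 2-year growth analysis, and they do not show that the trial's inference is invalid.

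**What to change.** In section 1.1 (Analyses for Hypothesis 1 of Aim 1) and section 17.1, name Group minus Self-Directed and Facilitated minus Self-Directed, on baseline-to-6-month change, as the planned contrasts that test the pre-post part of Hypothesis 1. State that both must be significant, because the hypothesis says both, and state whether they are one- or two-sided. Say that this applies to the parent-reported outcomes available at 6 months.

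In sections 1.1 and 17.2, keep the .81 but label it as omnibus interaction power, and report beside it the power for each contrast and for both. The omnibus F may remain as a gate; if it does, the joint power should be quoted with the gate in place.

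No extra families, visits or data are needed. The cost is a few sentences and a less favourable stated power figure for the 6-month claim.
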